More recently, a micropulse delivery mode of diode laser (Micropulse TSCPC, mTSCPC) has been used to treat glaucoma by ablating the ciliary processes and reduce aqueous humor production with more selective targeting and less collateral damage.¹³ In contrast to conventional laser delivery where a continuous flow of high intensity energy is delivered, micropulse laser application delivers a series of repetitive short pulses of energy with rest periods in between pulses. This allows energy to build up in the targeted pigmented tissues, eventually reaching the coagulative threshold, while the adjacent non-pigmented structures have time to cool off during the off cycle without reaching the point of coagulation.²⁰⁻²⁷

Only a few studies have described the outcomes of this novel glaucoma therapy, showing mTSCPC to have comparable efficacy with fewer side effects when compared with traditional continuous wave mode diode laser delivery.^{13-14,28} This improved side effect profile has the potential to make mTSCPC an earlier therapeutic option instead of reserving it exclusively for end-stage refractory eyes.

Purpose

The goal of this study is to evaluate the efficacy and safety of the novel form of trans-scleral cyclophotocoagulation using micropulse diode laser and trans-pars plana treatment (Micropulse TSCPC, mTSCPC MP3, IRIDEX CYCLO G6[™] Glaucoma Laser System, CA, USA).

The main outcome will be the efficacy of the mTSCPC MP3 evaluated by the short-term and long-term reduction of IOP and number of anti-glaucomatous drops used postoperatively. The other outcomes will be the safety of this device by looking at the possible decrease in corrected distance visual acuity (CDVA), the progression of the optic nerve cupping and the complications.

Study Design

This will be a prospective, interventional and monocentric study based in a university hospital setting.

Based on the established inclusion and exclusion criteria, the study investigators will enrol patients followed in their own clinic or new patients referred by other ophthalmologists. After learning and asking questions about the risks and benefits of participating in this study, patients will be requested to sign the appropriate information and consent form. They will then have a complete pre-interventional ophthalmologic evaluation including corrected distance visual acuity (CDVA), a complete slit-lamp biomicroscopy examination, an IOP measurement with the Goldmann applanation tonometer, a measurement of the central corneal thickness with a handheld pachymeter (IOPac Advanced, Heidelberg Engineering, Franklin, MA, USA), and a dilated fundus examination with a particular attention to the cup-to-disk ratio (CDR) of the optic nerve.

Population

A total of fifty (50) glaucoma patients will be included in this prospective study. They will be recruited by two (2) glaucoma specialists at the Notre-Dame Hospital department of ophthalmology (University of Montreal Hospital Center, CHUM). Patients will meet the inclusion and exclusion criteria listed below (Tables 1-2). Participants will undergo a micropulse transscleral cyclophotocoagulation (mTSCPC MP3) treatment session in the affected eye.

Table 1: Inclusion criteria
Patients of either sex and any race aged 18 years old and above.
Followed by a glaucoma subspecialist at University of Montreal Hospital Center.
IOP above target and unresponsive to maximal tolerated medical therapy with or without
previous surgical intervention.
a. mild glaucoma: IOP > 18 mmHg
 b. moderate glaucoma: IOP > 15 mmHg
c. advanced glaucoma: IOP > 12 mmHg
Considered poor candidates for additional filtering surgery or implantation of glaucoma
drainage devices.

Table 2: Exclusion criteria

Patients unable to give informed consent.

Patients with significant scleral thinning, defined as thinning of more than one clock hour noticed on scleral transillumination.

Ocular infection or inflammation in the study eye in the 2 months prior to enrolment. Intraocular surgery in the study eye in the 2 months prior to enrolment.

Baseline Parameters

The following baseline parameters will be recorded for each patient: age, gender, race/ethnicity, type of glaucoma diagnosis, ocular history (previous surgery and laser therapy), preoperative IOP, number of glaucoma medications prior to intervention, preoperative corrected distance visual acuity (CDVA), preoperative cup-to-disc ratio (CDR), pain level (using a verbal analog scale, see Table 3).

Table 3: Verbal analog scale for pain level	
Pain grade	Description of pain during laser, after subconjunctival anesthesia
None	No subjective feeling of pain.
Mild	Pain easily tolerable.
Moderate	Pain tolerable with difficulty.
Severe	Pain intolerable.

Treatment

The intervention will have to take place within thirty days following the screening appointment and will be executed by one of the two glaucoma specialists listed as the investigators of this study. The procedure will be done under local subconjunctival or rarely retrobulbar anesthesia.

All participants will have a treatment session of micropulse trans-scleral cyclophotocoagulation in the affected eye, using the MicroPulse[®] P3 Glaucoma Device (MP3) powered by the CYCLO G6[™] Glaucoma Laser System (Iridex, Mountain View, CA, USA).

Laser settings will be programmed as follows: power—2000mW-2500mW (average 2000mW) of 810nm infrared diode laser set on micropulse delivery mode; micropulse "on" time—0.5ms; micropulse "off" time—1.1ms; and duty cycle (proportion of each cycle during which the laser is on)—31.33 %.

The laser probe will be applied in a continuous sliding or painting motion from 9:30 to 2:30 and from 3:30 to 8:30. The 3 and 9 o'clock positions will be bypassed to avoid damage to ciliary neurovascular structures, as is standard technique with traditional continuous wave TSCPC. The probe will be applied perpendicular to the limbus with the edge directly on the limbus at all times (fiberoptic tip at 3 mm posterior to the limbus).

The laser will be delivered over 360° for 160–320s. Treatment duration will be adjusted based on iris color and glaucoma severity (mild glaucoma: 160s, moderate glaucoma: 240s, advanced glaucoma: 240-320s).

Post-Intervention Follow-Up

The patients will be seen by their attending ophthalmologist one (1) week, one (1) month, three (3) months, six (6) months, twelve (12) months and eighteen (18) months after the intervention. They will be seen more often if any complication occurs, in which case the frequency of their visits will be decided by their glaucoma specialist.

The following follow-up parameters will be recorded at each visit: postoperative IOP, number of glaucoma medications, corrected distance visual acuity (CDVA), cup-to-disc ratio (CDR), and presence of complications detected by a complete slit-lamp biomicroscopy examination. The pain level (using a verbal analog scale, see Table 3) will be assessed while performing the laser treatment.

A less than 25% reduction in IOP from baseline after 1 month on two consecutive visits separated by an interval of 1 week will be the basis for a second treatment. The same criteria will apply for third treatment if necessary. Repeat treatments will be done in the same conditions and settings as the primary treatment.

Primary and Secondary Outcomes

The primary outcome measure of success of this study will be defined as an IOP between 6 and 21 mmHg at final follow-up (18 months) with or without IOP lowering medications, at least 25% reduction in IOP at final follow-up compared to baseline, and no need for incisional glaucoma surgery during follow-up period. The need for a repeat micropulse TSCPC will not be considered a failure.

The secondary outcome measure of success will include the number of repeat treatments, the number of IOP lowering medications at 18 months, changes in CDVA (number of lines reduction or improvement from baseline), the progression of CDR compared to baseline, and the frequency of complications associated with the laser therapy (e.g., prolonged AC inflammation [cells 1+ or higher for more than 2 weeks with topical steroid eye drops], sympathetic ophthalmia, chronic hypotony, phthisis bulbi, scleral thinning).

The outcome of the therapy will ultimately be defined in terms of success rate, hypotony rates, response rates (success and hypotony rates considered together) and retreatment rates.

Statistical Analysis

Paired 2-tailed Student t-tests will be used to compare changes in IOP, number of glaucoma medications, CDVA and CDR between each time point. For each of these measures, a single factor analysis of variance will be realized. Snellen visual acuities will be converted to logarithm of the minimum angle of resolution (logMAR) values for statistical analysis. Bonferroni correction will be used to control the multiplicity of t-tests. Frequency distribution and percentage will be used for categorical data. Demographic analysis will use Wilcoxon rank-sum test for age and chi-square test for gender. Fisher's exact test will evaluate equivalence of glaucoma types. A level of $p \le 0.05$ will be considered statistically significant. Analysis will be done with the SPSS version 20.0 software (SPSS Inc., Chicago, IL, USA).

Benefits, Risks and Disadvantages

Benefits

Micropulse trans-scleral CPC is thought to be an effective strategy to reduce the intraocular pressure in patients who are poor candidates for additional filtering surgery or implantation of glaucoma drainage devices. This therapy is considered less invasive and associated with fewer side effects than the traditional trans-scleral CPC procedure.

By participating in this study, patients will contribute to the research community in the ophthalmology field. The results already published on the micropulse trans-scleral CPC are encouraging, but additional results regarding the efficacy and safety of this procedure will further support its beneficial use.

Risks

Participants are exposed to all conventional complications that may be associated with CPC: prolonged anterior chamber inflammation, sympathetic ophthalmia, chronic hypotony, phthisis bulbi, scleral thinning, decrease in visual acuity, pain. However, the side effect profile of micropulse CPC is thought to be better than conventional glaucoma surgeries and conventional CPC, which has been used for many years in the treatment of advanced glaucoma. In case of failure of micropulse CPC to control adequately the IOP, there is always a possibility to add topical or systemic medication, or to undergo another surgery if needed.

Disadvantages

The only disadvantage in participating in this study will be to come to the requested follow-up appointments, which do not imply any risky or painful procedure.

Confidentiality

Collected information will only be accessible by the investigators of this study, and only relevant data needed to achieve the scientific objectives of this project will be collected. No identifiable information will be stored in the documents of this study, as patients will be identified solely by a code number. The key of the code linking the identity of the participant to his research file will be retained exclusively by the principal investigator of this project. No nominative information will appear in the final results of this study. Research data may be published or scientifically discussed, but it will not be possible to identify participants.

Data will be stored in the research office of the principal investigator at the CHUM Ophthalmology Department, Notre-Dame hospital, Montreal (Quebec, Canada) on a single password-protected computer device (Removable HDD) for a period of 10 years, and then erased from the device.

Information and Consent Form

An information and consent form will be signed by all participants. Patients who refuse to participate in this study will have no prejudice and will receive the best standard of care from their attending ophthalmologist.

Scientific and Ethics Committees

This research project will be reviewed and approved by the CHUM local research ethics committee (CER).

Budget

MicroPulse® P3 (MP3) laser probes reusable for 5 patients each: 395\$/probe x 10 (primary treatment for 50 patients) = 3,950\$	
395\$/probe x 5 (for estimated repeat treatments) = 1,975\$	5,925\$
Total	
Patient recruitment and follow-up require the help of a research assistant for	
18 months (part-time)	1,500\$
Didactic material (posters, publications, presentations)	1,000\$
Statistical consultation	1,000\$
Other sources of funding	0\$
Total	9,425\$

References

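### Pain is named as a complication and complication frequency is a secondary outcome, but the plan has no defined route for recording pain after the procedure.

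*Combined protocol and SAP*

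**What the plan says.** All references are to the combined protocol and SAP.

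- **Benefits, Risks and Disadvantages (Risks)** gives the conventional complications to which participants are exposed. The list ends "chronic hypotony, phthisis bulbi, scleral thinning, decrease in visual acuity, pain".
- **Primary and Secondary Outcomes** makes the frequency of complications a secondary outcome and gives five examples, introduced by e.g. Pain is not one of them.
- **Baseline Parameters** includes "pain level (using a verbal analog scale, see Table 3". The heading of Table 3 is "Description of pain during laser, after subconjunctival anesthesia", with four grades: none, mild, moderate and severe.
- **Treatment** states: "The procedure will be done under local subconjunctival or rarely retrobulbar anesthesia".
- **Post-Intervention Follow-Up** sets visits at 1 week and at 1, 3, 6, 12 and 18 months, with extra visits if a complication occurs. Each visit records IOP, number of medications, CDVA, CDR and "presence of complications detected by a complete slit-lamp biomicroscopy examination". The next sentence says that the pain level "will be assessed while performing the laser treatment".
- **Statistical Analysis** plans counts and percentages for categorical data. It does not mention pain.

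**The concern.** The plan tells participants that pain is a possible complication and promises to report how often complications occur. It grades pain only in relation to the laser session, under local anaesthesia. A grade taken then says nothing about pain on later days. What is specified for the visits is an examination, and an examination does not elicit a symptom.

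Safety is a declared study outcome, and the Benefits text describes the method as having fewer side effects than conventional treatment. A safety table with no line for postoperative pain, or with a count built from what patients happened to mention, could not show whether pain was absent or was not asked about.

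**Working it through.** The plan states no figure on this point, so the check is a comparison of sections.

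**Step 1. Trace each complication named under Risks to the outcome list and to the visit list.**

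| Complication under Risks | In the secondary outcomes? | Stated way of recording it at follow-up |
|---|---|---|
| Prolonged anterior chamber inflammation | Yes | Slit-lamp examination |
| Sympathetic ophthalmia | Yes | Slit-lamp examination |
| Chronic hypotony | Yes | IOP at each visit |
| Phthisis bulbi | Yes | Slit-lamp examination |
| Scleral thinning | Yes | Slit-lamp examination |
| Decrease in visual acuity | Yes, as change in CDVA | CDVA at each visit |
| Pain | No | None |

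The slit-lamp entries repeat the plan's general statement on how complications are detected. They do not judge how well that works for each diagnosis. Six of the seven complications have both a named outcome and a stated follow-up method. Pain has neither.

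**Step 2. Count the planned pain assessments after the laser.** There are 6 scheduled visits and 50 patients, so 6 × 50 = 300 planned patient-visits. Visits with a pain item: 0 of 6. Planned patient-visits with a pain item: 0 of 300.

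**Step 3. Ask whether the baseline entry fills the gap.** It does not. A baseline grade is not a postoperative one. The entry also refers to Table 3, whose heading concerns pain during the laser, and the follow-up section gives that same timing. Read literally, the baseline pain level is therefore an intra-procedural grade. If a true pre-laser grade is intended, the heading of Table 3 does not fit it. The two sections need to be reconciled.

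**Step 4. Ask whether the analysis section fills the gap.** Counts and percentages would suit a pain grade, but no section links any pain grade to the complication outcome.

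**The case against.** The strongest reply is that the complication outcome is an open list and that extra visits are allowed when a complication occurs. A patient who returns with pain could be recorded. The slit lamp is also not the only route to a complication, since hypotony is established from the IOP measurement. This stands. A reader might infer that postoperative pain cannot appear in the complication frequency, and the documents do not support that. What they lack is a defined route. Volunteered reports would have no common question, grade, threshold or time window.

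Second, the Risks text gives pain no timing and may mean pain during the procedure, which the plan does grade. The documents do not settle this. The other items in the list are mostly conditions that persist after treatment, and the text does not restrict pain to the session. Even on the narrower reading, nothing carries the Table 3 grade into the complication outcome.

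Third, a reader might infer that pain is being measured when it is at its lowest, because the eye is anaesthetised. No section compares pain during the laser with pain later, so this cannot be claimed.

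Fourth, postoperative pain is not a declared endpoint, so adding it is partly a matter of scope. That is fair, and it is why the point ranks low.

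**Conclusion.** The concern holds in this form: pain is named as a complication, complication frequency is an outcome, and following the plan exactly would yield no systematic postoperative pain data at any of the six scheduled visits. A low or zero count from volunteered reports could not be read as absence of pain. The inconsistency between the baseline entry and Table 3 is a separate small defect in the text.

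The size is 0 of 6 visits. The amount of pain that would be missed cannot be estimated, because the documents give no postoperative pain rate. The conclusion assumes that the visit list is complete as written and that pain under Risks is not limited to the laser session. The primary outcome and the planned tests are unaffected. This is an inexpensive improvement, not a flaw that threatens the study.

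**What to change.** 1. In Baseline Parameters, state whether a pre-laser pain grade is intended. If so, record it before treatment on a copy of the four-grade scale whose heading is not tied to the laser. Keep Table 3 for pain during the laser.
2. In Post-Intervention Follow-Up, add the same question to each of the six scheduled visits with a stated recall period. At 1 week it should cover the whole time since treatment, because no earlier visit is scheduled. For later visits, state the period in advance and note whether a repeat laser session fell within it.
3. In Primary and Secondary Outcomes, say when pain counts as a complication.
4. In Statistical Analysis, report at each visit the number answering, the number and percentage with moderate or severe pain, and the number and percentage whose grade is worse than before the laser. Keep these rows separate from pain during the laser.

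The pre-laser grade matters because some patients may already have pain; this is an assumption, as the documents do not say. Without that grade, existing pain could be counted against the laser.

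The cost is one extra question per visit and one or two extra rows in the safety table, with no added visits. Because there is no control group, attribution of later pain to the laser would remain limited even with the pre-laser grade. If the investigators prefer not to collect these data, the plan and the report should state that postoperative pain was not assessed.

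### The primary success definition leaves continuous-wave CPC and other non-incisional pressure-lowering procedures unclassified, so an eye that has one can, read literally, count as an MP3 success

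*Combined protocol and SAP*

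**What the plan says.** The section Primary and Secondary Outcomes defines primary success by three conditions that must all hold:

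- an absolute range: "IOP between 6 and 21 mmHg at final follow-up (18 months) with or without IOP lowering medications";
- a relative fall: "at least 25% reduction in IOP at final follow-up compared to baseline";
- a surgical condition: "no need for incisional glaucoma surgery during follow-up period".

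One exemption follows: "The need for a repeat micropulse TSCPC will not be considered a failure". No other procedure is named as a failure or as exempt.

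Three other places bear on the third condition.

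- **Population, Table 1.** One entry criterion, covering filtering operations and drainage devices, reads in part "Considered poor candidates for additional filtering surgery or implantation of glaucoma".
- **Benefits, Risks and Disadvantages, Risks.** If micropulse CPC does not control the IOP adequately, the patient may have more medication "or to undergo another surgery if needed". The type of surgery is not specified. The same paragraph refers to "conventional CPC, which has been used for many years in the treatment of advanced glaucoma".
- **Post-Intervention Follow-Up.** The parameters listed for each visit are IOP, number of medications, CDVA, CDR and complications. Other glaucoma procedures are not listed, although previous surgery and laser therapy are recorded under Baseline Parameters.

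**The concern.** The Purpose section says the study is to evaluate the efficacy of MP3 micropulse treatment. There is one treated group and no control, so the 18-month success rate can be credited to the device only if the outcome rule separates its effect from that of any later procedure.

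The rule does this for incisional surgery. It deliberately does not do so for repeat micropulse, which is part of the treatment under study. Between these two lies a third class, non-incisional IOP-lowering procedures other than micropulse. Continuous-wave CPC is the one the protocol itself discusses, and the rule is silent on the whole class. If any eyes have such a procedure, the reported rate depends on how the analyst reads that silence, and the literal reading favours the device.

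The planned data may not allow a later correction, because no field for such procedures is described. The Statistical Analysis section also gives no rule for IOP values measured after another procedure.

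**Working it through.** **Step 1. Is there a figure to reproduce?** No. The documents give no expected success rate, no rescue rate and no derivation of the sample size. The only numerical input is the number of patients: "A total of fifty (50) glaucoma patients will be included in this prospective study".

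**Step 2. Apply the rule as written.** Take an eye that has continuous-wave CPC during follow-up and, at 18 months, has an IOP of 6 to 21 mmHg and a fall of at least 25%.

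| Condition | Result for this eye |
|---|---|
| IOP range at 18 months | met |
| At least 25% fall from baseline | met |
| Incisional-surgery condition | met, unless someone judges that such surgery was needed |
| Exemption for repeat micropulse | does not apply |

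Every stated condition is met, so the eye is a success. It would fail if it missed either IOP condition, so only rescued eyes that end within the limits are affected.

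**Step 3. Compare with the Risks section.** That section introduces further medication or surgery as what may follow when micropulse has failed to control the IOP. In that sense the eye in Step 2 is a micropulse failure, yet the outcome definition does not make it one.

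**Step 4. Size per eye.** Let *k* be the number of eyes that have such a procedure and still meet both IOP conditions, and *s* the number of successes under the literal rule. With one study eye per patient and all 50 analysed:

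- literal rule: *s*/50;
- rule that fails these eyes: (*s* − *k*)/50;
- difference: *k*/50, which is 1/50 = 2 percentage points per eye, whatever *s* is.

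Neither *s* nor *k* is in the documents. For illustration only, assume *s* = 30. Exact (Clopper-Pearson) 95% intervals are shown.

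| *k* (assumed) | Success rate if these eyes fail | 95% interval | Difference |
|---|---|---|---|
| 0 | 30/50 = 60% | 45.2 to 73.6% | 0 points |
| 1 | 29/50 = 58% | 43.2 to 71.8% | 2 points |
| 3 | 27/50 = 54% | 39.3 to 68.2% | 6 points |
| 5 | 25/50 = 50% | 35.5 to 64.5% | 10 points |

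The literal rule can only equal or exceed the other, so the direction is fixed. The size is not, and *k* = 0 is compatible with everything in the documents.

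**The case against.** The strongest reply has five parts.

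1. *Exempting repeat micropulse alone implies that other lasers do count as failure.* This is a fair inference, since the exemption would hardly be needed if no laser could be a failure. But no sentence says so, and the third condition names only incisional surgery. A primary outcome should not rest on an implication that points the opposite way from its literal wording.

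2. *The condition concerns need, not surgery performed.* An eye that needs incisional surgery but is unfit for it could therefore fail. This stands as a limit on the concern. It does not remove it, because the protocol does not say who judges need or by what standard.

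3. *No such rescue is planned.* This also stands. The documented response to an insufficient fall is a second and, if necessary, a third micropulse session. The Budget section pays for 5 further probes at 5 patients each, or 25 repeat uses. The remark on conventional CPC comes from a comparison of side effects and does not name it as rescue. Such procedures are not excluded either, since the further surgery allowed after failure is left open.

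4. *The follow-up list is not a full inventory.* It also omits repeat micropulse and incisional surgery, which the outcomes require. That is true, but those two are implied by the outcome definitions, whereas nothing implies recording the others.

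5. *No planned decision depends on the rate.* No benchmark or test is attached to it, and categorical data are to be reported as frequencies and percentages. This bears on severity.

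A reader might also infer that Table 1 disables the surgical criterion because the enrolled eyes will not have incisional surgery. The documents do not support that. Being a poor candidate is not an exclusion, the Risks section keeps surgery open, and poor candidacy lowers the chance of an operation rather than the need for one.

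**Conclusion.** The gap is real. Non-incisional IOP-lowering procedures other than micropulse are unclassified in the primary outcome and absent from the listed follow-up parameters. On the literal wording, an eye that has one and meets both IOP conditions at 18 months is an MP3 success, which sits badly with the protocol's own description of such eyes as cases of micropulse failure.

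The supported size is 2 percentage points per such eye, assuming 50 eyes analysed, and always in the device's favour. A reader might infer that the success rate will be inflated by some particular amount, or that continuous-wave rescue is expected. Neither follows: the documents give no rescue rate and plan no such rescue, so the effect may be nil.

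Severity: should-fix. It affects the primary outcome of a single-arm study and is cheap to settle in advance, but its frequency is unknown and no planned decision is shown to change. Confidence: moderate, because the exemption for micropulse and the reference to need allow a reading under which some of these eyes would already fail.

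**What to change.** Change the outcome classification only. No clinical rule is proposed, and the choice of any further treatment is untouched.

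- **Third component of primary success.** Keep the existing condition on incisional glaucoma surgery and add: *and no IOP-lowering procedure in the study eye other than protocol micropulse TSCPC, through 18 months*.
- **Exemption.** Keep the statement that repeat micropulse is not a failure.
- **Data.** At each visit, record the type and date of any IOP-lowering procedure in the study eye since the previous visit.

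The cost is one clause in the outcome definition and one dated field on the visit form. The downside is a possibly lower success rate, by 2 points for each eye reclassified out of 50. If no such procedure occurs, the rate is unchanged.

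### Does the 18-month success rate need a planned split by number of laser sessions, given that re-lasered eyes can still count as successes?

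*Combined protocol and SAP*

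**What the plan says.** Under Primary and Secondary Outcomes, success at 18 months has three parts: IOP of 6 to 21 mmHg with medication allowed, "at least 25% reduction in IOP at final follow-up compared to baseline", and no incisional glaucoma surgery during follow-up. The section then states that "The need for a repeat micropulse TSCPC will not be considered a failure".

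Under Post-Intervention Follow-Up, the basis for a second session is "A less than 25% reduction in IOP from baseline after 1 month on two consecutive visits separated by an interval of 1 week". For a further session, "The same criteria will apply for third treatment if necessary". Routine visits fall at "one (1) week, one (1) month, three (3) months, six (6) months, twelve (12) months and eighteen (18) months after the intervention". The Treatment section says "The intervention will have to take place within thirty days following the screening appointment", so the natural reading is that the 18 months run from the first session. No reset after a repeat is stated.

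Retreatment is reported in its own right: "The secondary outcome measure of success will include the number of repeat treatments", and the final list of rates includes "response rates (success and hypotony rates considered together) and retreatment rates". The Statistical Analysis section plans frequencies and percentages for categorical data. Neither section crosses success with number of sessions, and neither reports time since the last session.

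**The concern.** The retreatment trigger is the negation of one success component. An eye that has missed the 25% reduction on two visits can be treated again, up to twice, and then be scored on that same reduction at month 18. The headline rate therefore pools eyes treated once, twice and three times.

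The Purpose section makes both short-term and long-term IOP reduction the main outcome. Results at week 1 and month 1 come before any repeat and are unaffected. The long-term result is affected. A reader told only the success rate and the retreatment rate might take the success rate as what one session achieves, and could not recover the single-session figure from those two numbers. If repeats can also come late in follow-up, some 18-month readings might reflect a much shorter interval since the last laser.

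**Working it through.** **Inputs from the protocol.** Sample size: 50 patients (Population). Probes: 5 patients each, 10 for primary treatment and 5 for repeats (Budget). The budget reproduces: 10 × 5 = 50 primary sessions; 10 × $395 = $3,950; 5 × $395 = $1,975; sum $5,925. Five repeat probes cover up to 5 × 5 = 25 repeat sessions. That is 25 eyes with one repeat each, or 13 eyes if 12 have two repeats and one has one (12 × 2 + 1 = 25). This is purchase capacity, and actual use may be lower.

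**Inputs assumed.** The documents give no expected success or retreatment rate. I take S = 30 successes out of 50 (60%), all 50 eyes evaluable at month 18, and R retreated eyes. The success proportion in retreated eyes is k times that in the others, with k = 1 or 0.5.

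**Formula.** The success proportion in eyes treated once is p = S / ((50 − R) + kR), and single-session successes = (50 − R) × p.

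| R | k = 1 | k = 0.5 |
|---|---|---|
| 5 | 45 × 30/50 = 27.0 (54%) | 45 × 30/47.5 = 28.4 (57%) |
| 10 | 40 × 30/50 = 24.0 (48%) | 40 × 30/45 = 26.7 (53%) |
| 13 | 37 × 30/50 = 22.2 (44%) | 37 × 30/43.5 = 25.5 (51%) |
| 25 | 25 × 30/50 = 15.0 (30%) | 25 × 30/37.5 = 20.0 (40%) |

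Percentages are of all 50 eyes. The gap from the 60% headline runs from about 3 points (R = 5, k = 0.5) to 30 points (R = 25, k = 1).

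**Limits without any assumption on k.** Single-session successes lie between max(0, S − R) and min(S, 50 − R). For S = 30 and R = 25 this is 5 to 25, or 10% to 50%. The two margins do not fix the overlap.

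**How plausible the large gap is.** The 30% figure needs the whole repeat budget used on 25 different eyes. It also needs eyes selected for poor response to do as well at month 18 as eyes never retreated. In that case 25 − 15 = 10 never-retreated eyes must fail at month 18. If repeats are allowed throughout follow-up, those 10 would have to lose control late, leave the 6 to 21 mmHg range, need incisional surgery, or meet the trigger without being re-lasered. The 10% limit is less plausible still: 25 of 25 retreated eyes would succeed but only 5 of 25 others.

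**Timing.** One week is 7/30.44 = 0.23 month. If the trigger is assessed about one month after each session, repeats fall near 1.23 and 2.46 months and leave 16.8 and 15.5 months to the final reading. If it can be met at any time after month 1, a trigger at month 12 with laser on the confirmation day leaves 18 − 12 − 0.23 = 5.8 months. Timing therefore matters mainly on the open-ended reading.

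**The case for a change.** The strongest case for a change is that success after one session is a natural question about a laser procedure, and that the single-session rate can only equal or fall below the headline. Leaving that table out of the plan means the decision to show it is taken once results are known. The cost would be small: one descriptive table and a date for each session. The budget labels its five extra probes as being for estimated repeats, so the sponsor does expect some retreatment.

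Much of this stands. The cross-tabulation is not pre-specified, and the two planned rates cannot replace it. But the plan does not conceal retreatment. It declares how repeats are handled and makes their number and rate reported outcomes. To report these, the analysts must know each eye's number of sessions and its success status, and those two facts are all the table needs.

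The table would also answer less than it seems to. Session number is decided by IOP response after baseline, so the groups with one, two or three sessions are selected by response and cannot be compared as an effect of sessions. Cells would be small: 15 of 25 has a 95% Wilson interval of 41% to 77%. Medication may be added and is allowed within success, so control could not be credited to laser alone. Eyes missing at month 18 would need a counting rule before a percentage of all 50 meant anything.

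**Conclusion.** No change to the plan is needed. The primary outcome is a declared and legitimate one: control at 18 months under laser with repeats as needed. Followed as written, the plan gives a sound rate for that strategy, with the retreatment rate beside it. No bias, arithmetic error or contradiction in the primary endpoint was found, and no planned result would change.

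What remains is a reporting preference. On the assumptions above, the difference between the headline and single-session success could be about 3 to 30 points, depending mostly on a retreatment rate that the documents do not give. Analysts can reasonably show 18-month success by number of sessions when they report. They should then say that the groups are defined by response, that the cells are small, and how eyes missing at month 18 are counted. Time since the last session is secondary, because on the narrow reading of the trigger at least about 15.5 months remain.

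Separately, the text on the retreatment trigger and the routine visit list could be reconciled, since the list has no pair of visits one week apart. A conditional confirmation visit is compatible with a routine schedule, so this does not disturb the conclusion.
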